11.1 Eligibility screening process

Refer to section 8.5.

11.2 Informed consent

Refer to section 17.2.

11.3 Measures taken to minimise bias

11.3.1 Randomisation/Blinding/Deblinding

All patients (n=97) will be randomized (1:1) to either immediately receiving golimumab monotherapy (n=48) (the “TNFi-induction”-group), or to the step-up regimen with csDMARDs (n=47) (“csDMARD-Step-up”-group) in a double-blind, double-dummy design.

The “TNFi-induction”-group will receive the standard golimumab dose of 50 mg subcutaneously (SC) every 4 weeks (with matching csDMARD-placebo capsules).

In the “csDMARD-Step-up” regimen, patients will start with oral methotrexate (MTX) capsules at a weekly dose of 15 mg for 4 weeks (with matching “golimumab”-placebo injections). In case of intolerance or toxicity to MTX or MTX placebo, the weekly dose of MTX or MTX placebo can be tapered to 10 mg at week 4, with a further possible reduction to 7,5 mg at week 8; in case of persistent intolerance/toxicity, MTX or MTX placebo will be stopped at week 12. When there are no tolerability/toxicity issues, the weekly dose of MTX or MTX placebo will be increased to 20 mg at week 4 (with an option to again reduce the dose in case of intolerance/toxicity).

At week 12, “Patient Acceptable Signs & Symptoms Improvement” (“PASSI”) will be assessed (see Addendum 3) in order to determine the need for additional, open-label “escape” csDMARD treatment: in case of an acceptable improvement, blinded study medication will be continued until week 24; if there is no satisfactory response, oral sulphasalazine can be added to the blinded study medication at a dose of 2 g per day (escape medication).

The randomization to either the “TNFi induction”-group or the “csDMARD Step-up”-group will be done at the UZ Ghent Pharmacy and the randomization list will be kept there. If according to the data entered in the eCRF, the patient is eligible for randomization, the RedCap system will send a notification to the coordinating study team. Upon review of the screening visit data (including in- and exclusion criteria), the coordinating study team will approve randomization in the eCRF. This will trigger communication with the UZ Ghent pharmacy who will randomize the patient. The local site will be informed via an email and the eCRF system. The UZ Ghent Pharmacy will assemble patient-specific medication kits that will contain (according to the randomization list) the golimumab/placebo syringes for each individual patient. When a new patient is to be randomized, the kits will be sent to the site containing:

- 7 golimumab/placebo syringes:
 - o 6 syringes for administration at baseline and weeks 4, 8, 12, 16 and 20.
 - o 1 spare syringe:
 - To be used in case of a problem with the first 6 syringes.
 - This syringe will be administered at week 24 in case the patient would need to continue at week 24 for another 12 weeks with blinded study

drug. In that case 2 more golimumab/placebo syringes will be distributed for administration on weeks 28 and 32.

At the time of randomisation of a first patient the site will receive a number of methotrexate and placebo bottles provided with a randomisation number. This medication is not patient-specific and will be allocated per study visit.

At the start of the study, the UZ Ghent Pharmacy will send the unblinding information, in a sealed envelope, to the national coordinating investigator conform the GMP regulation. If the local investigator would feel that unblinding of study medication has become necessary, the national coordinating investigator at UZ Ghent should be contacted to discuss the case (see contact information paragraph 15.3). If necessary, the coordinating investigator at UZ Ghent can unblind the patient in question and send notification thereof to HIRUZ and the UZ Ghent Pharmacy.

The study code should only be broken for valid medical or safety reasons, e.g. in the case of a severe adverse event where it is necessary for the investigator or treating health care professional to know which treatment the subject is receiving before he or she can be treated. If possible, other study team members should remain blinded.

The code breaks for the trial are kept in a separate study binder. The binder is located in a locked cupboard that only the study staff have access to. In the event a code is required to be unblinded a formal request for unblinding will be made by the local PI to the Coordinating Investigator (CI).

The CI/PI documents the breaking of the code and the reasons for doing so on the eCRF/study documents, in the site file and medical notes. It will also be documented at the end of the trial in any final study report and/or statistical report.

The study team will notify the Sponsor in writing as soon as possible following the code break detailing the necessity of the code break.

As the investigator is responsible for the medical care of the individual study subject (Declaration of Helsinki §3 and ICH 4.3) the coding system should include a mechanism that permits rapid unblinding (ICH GCP 5.13.4). The investigator cannot be required to discuss unblinding if he or she feels that emergent unblinding is necessary.

Patients for whom the medication is unblinded will be discontinued from the clinical trial.

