7.1 Study design description

The SPARTACUS clinical trial is a prospective, randomized, active-comparator controlled, double-blind, double-dummy, phase III, national multicentric clinical trial which consists of 2 phases (duration phase A is up to 60 weeks, phase B up to 3 years):

SPARTACUS Phase A: “Remission-Induction Phase”:

[figure not shown]
(Baseline to (maximum) week 60: for a global overview see Addendum 2)

All patients (n=90) will be randomized (1:1) to either immediately receiving TNFi (golimumab) monotherapy (“TNFi Induction”-group) (n=45), or to the step-up regimen with csDMARDs (“csDMARD Step-up”-group) (n=45) (figure 1).

Synovial biopsies will be harvested during the screening period by ultrasound (US) guided biopsy for small joints (Metacarpophalangeal- (MCP) and proximal interphalangeal- joints (PIP) of the hands, metatarsophalangeal joints (MTP) of the feet) or certain large joints (elbow, wrist, knee, ankle). In case of multiple small joint involvement, a joint with a score of 2 or more on Grey Scale/Power Doppler US assessment will be chosen to sample.

The patients in the TNFi-induction group will receive golimumab at a standard dose of 50 mg subcutaneously (SC) every 4 weeks (with matching methotrexate (MTX)-placebo) (figure 1). In case of potential intolerance or toxicity to MTX-placebo (see paragraph 9.5.8 for known side effects of MTX) , the dose will be gradually tapered to a minimum of 7.5 mg per week. When there are no tolerability/toxicity issues, the weekly dose of MTX-placebo will be increased to 20 mg at week 4.

Figure 1: Baseline – Week 8

[figure not shown]

¹“Blinded MTX-Intolerance”-regimen can be initiated from week 4, but also at later study visits.

²In case of intolerance to MTX-Placebo 20 mg QW, the previous dose (15 mg) can be used.

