8.1 Number of subjects and planned recruitment rate

In total it is expected to recruit 110 patients, of which 90 patients will be randomized in this trial and reach the primary endpoint timepoint (taking into account screen failures and drop outs) They will be recruited in rheumatology departments of different hospitals. At the UZ Ghent, the UZ Leuven and ZNA Jan Palfijn sites synovial biopsy sampling units are operational. The inclusion of patients is competitive, meaning that there are no minimum or maximum quota for inclusions per center.

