8.3 Withdrawal and replacement of subjects

8.3.1 Withdrawal of subjects

Subjects are free to withdraw from participation in the trial at any time. A subject must be discontinued from the trial if *the subject* withdraws consent. The reason why a subject withdraws consent, if given, must be recorded in detail in the electronic Case Report Form (eCRF) and in the subject's medical records. The already gathered subject data should remain in the trial database.

However, subjects can choose to discontinue trial treatment or interventions, but remain in the trial for other assessments or data collection, if applicable. The reasons for a subject to withdraw from trial treatment, if given, must be recorded in detail in the electronic Case Report Form (eCRF) and in the subject's medical records. The subject data should be collected in the eCRF.

An investigator may discontinue trial treatment for a subject for the following reasons:

- Pregnancy;

- Significant trial intervention non-compliance;
- If any clinical adverse event (AE), laboratory abnormality, or other medical condition or situation occurs such that continued participation in the trial would not be in the best interest of the subject;
- Disease progression which requires discontinuation of the trial intervention;
- If the subject meets an exclusion criterion (either newly developed or not previously recognized) that precludes further trial participation;
- Subject unable to receive study intervention for a duration of at least 3 months

The reasons for withdrawing a subject from study treatment must be recorded in detail in the electronic Case Report Form (eCRF) and in the subject's medical records. However, even if trial treatment is discontinued, the subject will remain in the trial and other assessments or data collection should be done, if applicable. The subject data should be collected in the eCRF.

A subject will be considered lost to follow-up if he or she fails to return for 2 consecutive scheduled visits and is unable to be contacted by the trial site staff.

The following actions must be taken if a subject fails to return for a required trial visit:

- The site will attempt to contact the subject and reschedule the missed visit as soon as possible and counsel the subject on the importance of maintaining the assigned visit schedule and ascertain if the subject wishes to and/or should continue in the trial;

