8.3.2 Replacement of subjects

Drop-out subjects that were randomized and have received at least one dose of study drug, will not be replaced.

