Samples will be stored for max. 10 years upon collection of each individual sample until downstream analyses (as defined in the protocol) are performed.

Unused, leftover material will be transferred to the “Biobank van menselijk lichaamsmateriaal van patiënten met reumatische en/of musculoskeletale aandoeningen en gezonde controles” (under supervision of [name]. [name]) upon appropriate written informed consent.

13 Statistical considerations

13.1 ***Sample size calculation, power calculation, significance level***

The primary end point of SPARTACUS is the percentage of patients going into remission.

The sample size for SPARTACUS was calculated based on the percentage of patients that went into clinical remission (TNFi versus placebo) in the CRESPA trial: 75% in the TNFi group versus 20% in the placebo group. Currently, there are no data in peripheral Spondyloarthritis regarding the percentage of patients going into clinical remission under a treatment with Methotrexate. There are also no data regarding differences in treatment effect regarding symptom duration: <3 months versus >3 months. Therefore, we estimated an expected 30% difference in percentage of patients going into clinical remission between both groups (MTX versus TNFi): 20% versus 50%. A sample size of at least 45 patients in each group is sufficient to obtain 80% power or more to detect a difference in proportions of 30% (20% versus 50%) at the alpha level of 5% using a Fisher's exact test.

13.2 ***Type of statistical methods and team***

The primary endpoint of SPARTACUS is to compare the proportion of patients achieving clinical remission, defined as absence of arthritis, enthesitis and dactylitis at week 24, in the “TNFi induction”-group versus the “csDMARD Step-up” group. This will be done using appropriate statistical methods. Statistical tests and evaluations will be performed by [name] and [name] (Ghent University Hospital, Department of Rheumatology); where appropriate, expert statistical advice will be sought ([name], Ghent University Hospital, Department of Medical Statistics).

In addition to this, several secondary endpoints will be evaluated:

- Comparison between the “TNFi induction” group and the “csDMARD Step-up” group regarding:

- Achievement of “sustained clinical remission” at week 24 (and week 36 for the patients remaining on blinded study medication).

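### The number to be randomised is 90 in section 7.1 and 97 in section 11.3.1, where the two arms add to 95; section 8.1 does not settle which is meant

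*Protocol*

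**What the plan says.** The protocol gives the size of the randomised population in several places.

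- **Section 7.1 (study design):** "All patients (n=90) will be randomized (1:1) to either immediately receiving TNFi (golimumab) monotherapy" or the step-up regimen, with 45 in each arm.
- **Section 11.3.1 (randomisation and blinding):** "All patients (n=97) will be randomized (1:1) to either immediately receiving golimumab monotherapy (n=48"), "or to the step-up regimen with csDMARDs (n=47").
- **Section 8.1 (number of subjects):** 110 are expected to be recruited, of which "90 patients will be randomized in this trial and reach the primary endpoint timepoint (taking into account screen failures and drop outs").
- **Section 13.1 (sample size):** "A sample size of at least 45 patients in each group is sufficient to obtain 80% power or more" for 20% versus 50% remission, using Fisher's exact test at 5%.

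Three further rules bear on how the number randomised relates to the number with a week 24 outcome.

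- **Section 8.3.2:** "Drop-out subjects that were randomized and have received at least one dose of study drug, will not be replaced".
- **Section 8.3.1:** "even if trial treatment is discontinued, the subject will remain in the trial and other assessments or data collection should be done".
- **Section 11.3.1:** "Patients for whom the medication is unblinded will be discontinued from the clinical trial".

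No numerical drop-out rate is given.

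**The concern.** Sections 7.1 and 11.3.1 both state how many patients in all will be randomised, and they give different numbers. Section 11.3.1 also disagrees with itself, because its arms do not add to its total. Section 8.1 might have reconciled them, but it uses one figure for two quantities that its own mention of drop-outs implies are different.

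The randomised total decides when enrolment stops and how long the pharmacy's randomisation list must be. Section 8.1 makes recruitment competitive with no quota per centre, so only the overall total limits enrolment. The same choice decides whether the 45 per group in section 13.1 is a number randomised or a number evaluable, and so whether the stated power holds before or after drop-outs.

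**Working it through.** **Inputs.** Totals and arm sizes come from sections 7.1 and 11.3.1. The recruited number and the week 24 number come from section 8.1. Rates (20% and 50%), test and alpha come from section 13.1. Section 13.1 does not say whether the test is one- or two-sided; two-sided is assumed here.

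**1. The protocol's own sample size.** Power was obtained by listing every possible pair of remission counts, applying the two-sided Fisher test to each table, and adding the binomial probabilities of the tables with p ≤ 0.05. At 45/45 the power is 81.5%. The continuity-corrected normal formula also gives 45 per arm. Section 13.1 therefore reproduces.

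**2. The counts.**

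- Section 7.1: 45 + 45 = 90. It adds up.
- Section 11.3.1: 48 + 47 = 95, which is 2 short of its own 97 and 5 more than the 90 in section 7.1.
- A 1:1 split of 97 is 49 + 48.

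**3. The two readings of section 8.1.**

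- *90 is the number reaching week 24 after drop-outs.* More than 90 must then be randomised, because dosed drop-outs are not replaced. Section 7.1, which puts all randomised patients at 90, is then wrong.
- *90 is the number randomised.* Section 11.3.1 is then wrong, and section 8.1 leaves no room for the drop-outs it mentions.

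Under the first reading, the losses the candidate totals would allow are:

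- from 95: 5/95 = 5.3%
- from 97: 7/97 = 7.2%
- from 90: none

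**4. Power at each candidate total, no drop-out** (arms listed as TNFi/csDMARD):

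| Randomised | Split | Exact Fisher power |
|---|---|---|
| 90 | 45/45 | 81.5% |
| 95 | 48/47 | 84.4% |
| 97 | 49/48 | 85.4% |

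**5. Conditional on drop-out.** The protocol gives neither a rate nor a handling rule here, so both are assumptions made for illustration.

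*(a) Drop-outs counted as not in remission.* Both remission rates are multiplied by (1 − d), with the same d in each arm. At d = 5% the rates become 0.50 × 0.95 = 47.5% and 0.20 × 0.95 = 19%.

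| Randomised | Power falls below 80% at d of about | Other values |
|---|---|---|
| 90 (45/45) | 2.3% | 78.0% at d = 5%; 74.0% at d = 10% |
| 95 (48/47) | 7.1% | 81.2% at d = 5.3% |
| 97 (49/48) | 8.7% | 81.0% at d = 7.2% |

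*(b) Drop-outs excluded.* Equal splits give 80.2% at 44/44, 79.6% at 43/43 and 78.3% at 42/42. Unequal splits fall on both sides of 80%: 42/43 gives 82.7% and 41/42 gives 81.6%, but 42/41 gives 79.8% and 41/40 gives 78.3%. This scatter comes from the discreteness of the exact test, so series (b) should not be read as a smooth decline.

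**The case against.** The strongest reply has four parts.

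- **Section 8.1 can be read as consistent with most of the protocol.** If 90 patients are both randomised and reach week 24, then 90 is the number of completers, the number randomised may be larger, and sections 8.3.2 and 13.1 fit. This reading is available, and it narrows the hard contradiction to section 7.1 against section 11.3.1 and to 95 against 97 within section 11.3.1. It does not remove that contradiction, because section 7.1 still puts all randomised patients at 90.
- **The operational risk is limited.** The coordinating team approves each randomisation, the hospital pharmacy holds the list, and sites have no quotas, so no site works to a total of its own. This stands. The uncertainty sits with the coordinating team and the pharmacy, who do need one number.
- **The primary inference is safe at full enrolment.** Every candidate total exceeds 80% power. This also stands. In addition, section 8.3.1 keeps patients who only stop treatment under assessment, so stopping treatment is not the same as losing the outcome. Unblinded patients do leave the trial, so the number randomised and the number reaching week 24 need not be equal.
- **The slip looks clerical, and drop-out handling belongs in the analysis plan.** One changed digit would make section 11.3.1 add up (97 to 95, or 47 to 49), and sections 7.1, 8.1 and 13.1 all use 45 or 90. The text still does not show which total is intended. How missing outcomes are analysed can be left to the analysis plan, but that plan cannot correct enrolment counts that the protocol states in conflict.

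**Conclusion.** The point holds and must be fixed. The protocol gives 90 and 97 for the same quantity, and the arms listed under 97 add to 95. These are facts of the current text and need no assumption. Section 8.1 does not resolve the conflict on either reading.

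The spread between the lowest and highest total is 7 patients. The sample size calculation in section 13.1 is correct for 45 analysed per arm, assuming a two-sided test, and all three candidate totals meet it before drop-out. The rating rests on the conflicting counts and not on a demonstrated loss of power.

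The drop-out figures rest on assumed rates and handling. They show only why the choice is not neutral: with drop-outs counted as non-remission, 90 randomised tolerates about 2.3% drop-out before power falls below 80%, against 7.1% for 95 and 8.7% for 97.

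**What to change.** 1. State one number to be randomised, with arm sizes that add up to it: 90 = 45 + 45, 95 = 48 + 47, or 97 = 49 + 48. The choice is the sponsor's. Use it in sections 7.1, 8.1, 11.3.1 and 13.1.
2. In section 8.1, give three separate figures: recruited (110), randomised, and expected to reach week 24. State the assumed drop-out rate that links the last two.
3. In section 13.1, say whether 45 per group is randomised or evaluable. If 90 is kept as the number randomised, state that the 80% power claim applies to 45 evaluable per group, and give the power at the sponsor's own assumed drop-out rate.

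The cost is protocol wording only. The effect size, test, alpha, endpoint and section 13.1 calculation stay as they are.

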6.1 Primary end points

The primary endpoint of the study will be the comparison between the 2 treatment strategies at week 24 with regard to achievement of clinical remission (defined as complete absence of arthritis, dactylitis or enthesitis on clinical examination). At the week 24 timepoint, there are 3 possible scenario's (figure 3):

1. In patients that do not reach a state of clinical remission at week 24, blinded study medication will be interrupted and all patients will start open-label SC golimumab for an additional 36 weeks (up to max. week 60).
2. In patients that achieve sustained clinical remission at week 24, defined as absence of clinical arthritis, enthesitis and dactylitis at both week 12 and week 24, all study medication will be discontinued and prospective follow-up will be planned in SPARTACUS Phase B.
3. In patients that reach a state of clinical remission at week 24, but that did not yet reach this status at week 12, blinded study medication will be continued without any change in the treatment schedule for another 12 weeks.

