8.3.3 Follow-up of withdrawn subjects

Regardless of the reason for withdrawal, the Principal Investigator (PI) must consider the following:

- Procedures for safe discontinuation of treatment;
- Retention and use of the data already collected.
- In case of withdrawing from study treatment, continue other assessments or data collection, if applicable.

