 - Safety: at the discretion of the treating rheumatologist (depending on the use of e.g. sulphasalazine escape medication).
- Dispensation of study drug:
 - Administration of Golimumab/Placebo injection at study site.
 - Dispensation of Placebo/Methotrexate capsules for weekly intake at home.
Dose according to tolerance (see Addendum8).

Phase A – Visit 8: WEEK 24 (+/- 1 week)

- Assessment of adverse events.
- Tuberculosis Questionnaire.
- Current medication (dose and duration).
- Study drug accountability.
- Patient reported outcomes (see Addendum 7):
 - Patient global assessment of disease activity (0-10 numerical rating scale).
 - Patient global assessment of pain (0-10 numerical rating scale).
 - Bath Ankylosing Spondylitis Disease Activity Index (BASDAI).
 - Bath Ankylosing Spondylitis Functional Index (BASFI).
 - Health Assessment Questionnaire (for SpA) (HAQ(-SpA)).
 - Assessment of SpondyloArthritis international Society (ASAS) Health Index (ASAS-HI).
 - “Health Economic Evaluation”: EuroQoL 5 dimensions, co-morbidity Index (SCQ) and healthcare utilization and productivity (in the past 3 months)
- Targeted physical examination.
- Vital signs (blood pressure, heart frequency).
- Weight.
- Smoking/alcohol status
- Rheumatological examination (see Addendum 5):
 - 78-Tender and 76-swollen joint count.
 - Dactylitis assessment.
 - Enthesitis assessment (SPARCC Enthesitis Index).
 - Bath Ankylosing Spondylitis Metrology Index (BASMI), including tragus-to-wall distance, lumbar flexion (Schöber index), lumbar lateroflexion, cervical rotation and intermalleolar distance; chest expansion.
 - Psoriasis skin evaluation (if applicable).
 - Physician global assessment of disease activity (0-10 numerical rating scale).
- Laboratory investigation:
 - Disease activity: ESR, CRP.

- Safety: peripheral blood count, serum creatinine, uric acid, liver function tests (ALT, gamma-GT, Alkaline Phosphatase, LDH), Creatine Kinase.
- Research samples (4 x 8ml blood-CPT and 10ml serum if treated in UZ Ghent or UZ Leuven)
- Trial continuation evaluation based on clinical remission (yes/no) at week 24 and potential sustained clinical remission (at week 12 and 24):
 - No clinical remission: stop blinded study medication; start open-label golimumab 50 mg SC every 4 weeks.
 - Clinical remission (but not sustained remission): continuation of the same blinded study medication.

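### Protocol 11.3.1 takes every unblinded patient out of the trial, so a code break earlier than the week-24 window means the week-24 remission examination is not held

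*Protocol*

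**What the plan says.** Section 11.3.1 limits code breaks: "The study code should only be broken for valid medical or safety reasons". It asks that the knowledge be contained: "If possible, other study team members should remain blinded". It then ends participation: "Patients for whom the medication is unblinded will be discontinued from the clinical trial". The wording is trial, not treatment, and it carries no exception for data collection.

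Section 8.3.1 treats stopping treatment and leaving the trial as different things. Among the grounds on which an investigator may stop treatment is: "If any clinical adverse event (AE), laboratory abnormality, or other medical condition or situation occurs" (with the condition that continuing would not serve the patient's interest). For patients taken off treatment it says: "even if trial treatment is discontinued, the subject will remain in the trial and other assessments or data collection should be done, if applicable". Withdrawal of consent is the only case in which it says that a subject must leave the trial. Unblinding appears in neither list. Section 8.3.3 repeats the retention rule: "In case of withdrawing from study treatment, continue other assessments or data collection, if applicable".

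The primary outcome (section 6.1) is clinical remission at week 24, meaning "complete absence of arthritis, dactylitis or enthesitis on clinical examination". It is read at Visit 8 in section 11.4.1, which includes a "Trial continuation evaluation based on clinical remission (yes/no) at week 24" and has a window of ±1 week.

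Three other provisions bear on the point. Visit 12 in section 11.4.1 doubles as the early discontinuation visit and includes the joint, dactylitis and enthesitis examination. Section 8.3.2 does not replace drop-outs who were randomised and dosed. Section 8.6 lets patients who leave the trial be followed in a separate cohort if they consent.

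**The concern.** The protocol takes care to keep observing patients who stop treatment, and an adverse event is one of the grounds it names. A severe adverse event is also its example of a reason to break the code. Take two patients with the same event, both taken off treatment. As written, the one whose code stays closed remains due for the week-24 examination, while the one whose code was opened leaves the trial. No passage says why they should differ.

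What is lost is the observation itself. An analysis plan can state how a patient without a week-24 status is counted, as section 10 already does for patients who received joint injections. It cannot supply an examination that the protocol ended. The patients affected are not a random subset, because the code may be opened only on medical or safety grounds.

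The other exits do not raise the same issue. Loss to follow-up (8.3.1) concerns patients who cannot be reached. The exits based on the PASSI question come at week 36 or 48, after the primary endpoint.

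**Working it through.** **1. The plan's own figure.** Section 13.1 states at least 80% power with 45 per arm for 20% versus 50%, Fisher's exact test, alpha 5%. Enumerating both binomial distributions, with a two-sided test assumed, gives 81.5% at 45/45. The figure reproduces.

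**2. Why no power claim follows.** With one patient fewer, exact power is 82.9% at 44/45 and 84.4% at 45/44 (csDMARD/TNFi), and 80.2% at 44/44. The rises come from the discreteness of the exact test. The protocol gives no code-break rate, so an expected loss of power cannot be derived from it.

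**3. Weight of one uncollected status.** Weight = 1 / patients per arm.
- 1/45 = 2.2 percentage points of an arm's remission rate.
- Section 11.3.1 gives arm sizes of 48 and 47: 1/48 = 2.1 and 1/47 = 2.1 points.

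This is the weight of any single missing patient in an arm of this size. It is a scale, not an estimate of bias.

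**4. Examinations forgone per code break.** Section 11.4.1 schedules the joint, dactylitis and enthesitis examination after baseline at weeks 4, 8, 12, 16, 20 and 24, which is 6 examinations. The early discontinuation visit, if held, gives one back. Net loss = scheduled examinations remaining to week 24, minus 1.

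| Code break | Remaining to week 24 | Net of exit visit |
|---|---|---|
| Before week 4 | 6 | 5 |
| After week 4, before week 8 | 5 | 4 |
| After week 8, before week 12 | 4 | 3 |
| After week 12, before week 16 | 3 | 2 |
| After week 16, before week 20 | 2 | 1 |
| After week 20 | 1 | 0 |

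The last row needs care. After week 20 the count nets to 0, but the exit examination serves as the week-24 examination only if it falls in the window, weeks 23 to 25 (24 ± 1). Between week 20 and week 23 the number of examinations is unchanged while the week-24 status is still missing. An exit before the week-12 window also forgoes the week-12 status that section 6.1 uses for sustained remission.

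**5. The passages side by side.**
- 8.3.1 and 8.3.3: treatment stopped, patient stays, assessments continue where applicable.
- 11.3.1: code opened, patient leaves the trial.
- 8.3.3 does not rescue the second case, because its continuation clause applies to withdrawal from treatment only.
- Cohort follow-up under 8.6 needs separate consent, lies outside the trial and has no stated week-24 visit.

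The week-24 examination is therefore secured for an unblinded patient only when the exit visit happens to fall in the window.

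**The case against.** The strongest reply is that this is a deliberate design choice. The rule sits under the heading on minimising bias (11.3). The primary outcome is a clinical examination, the local investigator is the one who requests the code break, and no independent blinded joint assessor is described. Other staff stay blinded only where possible, so a blinded examiner may not exist at every site. Much of this stands: some retained examinations would be done by someone who knows the arm. It does not defeat the point, because a flagged examination can be set aside in the analysis, whereas an absent one cannot be restored.

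A reader might infer that 11.3.1 flatly contradicts 8.3. The documents do not support that. 8.3.1 and 8.3.3 govern patients who stop treatment, their duty is qualified, and 11.3.1 can stand beside them as a specific rule for a different event. What is missing is a cross-reference and a reason.

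A reader might also infer that every code break before week 24 loses the primary examination, or that all remaining examinations are lost. Neither holds: the exit visit includes the same examination and may fall inside the window.

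Two further replies stand in part. If the analysis plan counts unblinded patients as non-responders, the extra examination would not change that analysis, though it would remain available for others. And safety is largely covered without any change, since section 15.8 follows serious adverse events to resolution, stabilisation or explanation.

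**Conclusion.** The point holds as a cheap improvement. As written, a code break earlier than the week-24 window ends collection of the primary outcome in a patient selected on a medical or safety event, and no analysis rule can recover it. The net loss per patient, if the exit visit is held, is 5 scheduled examinations at most and 0 at least; each missing week-24 status carries about 2 points of an arm's remission rate.

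This assumes that 11.3.1 is followed literally. How many patients are affected is unknown and probably few. It would be tempting to conclude that power is eroded or that the comparison is biased towards one arm. The protocol gives no code-break rate, no split by arm and no link between code breaks and remission, so neither conclusion is supported. Code breaks after the week-24 examination do not touch the primary outcome.

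**What to change.** Reconcile 11.3.1 with 8.3.1 and 8.3.3 for data collection only. One qualifying sentence after the discontinuation rule would do, for example: *For data collection (see 8.3.1 and 8.3.3), an unblinded patient who has not withdrawn consent continues the scheduled joint, dactylitis and enthesitis examinations at least to week 24, performed where possible by an existing team member who remains blinded; the eCRF records when the examiner knows the arm.* If the sponsor prefers to keep full discontinuation, 11.3.1 should say that it is a deliberate exception and give the reason.

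Treatment after unblinding is not addressed here. That includes the dispensing and treatment-allocation steps of the same visits, which the sponsor would need to separate from the assessments when wording the change. How these patients are analysed is left to the SAP.

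The cost is one sentence and one eCRF flag, using existing staff. If the change counts as substantial, section 17.3.2 requires a written, approved modification. The downside is up to 6 already scheduled visits per patient, and some examinations by an examiner who knows the arm.
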